4.3 Response Assessment

All patients participating in this study will undergo response assessments through evaluation of clinical findings and bone marrow/peripheral blood cell counts and morphology. Criteria to guide the investigator's assessment of response are defined in Table 3 below and Appendix 7 and Appendix 8.

Bone marrow for response assessment is required at:

C2D1 if no peripheral blasts; otherwise, at C3D1, regardless of peripheral blast count
 Not applicable for patients enrolled after Protocol Version 7/ Amendment 6

- For patients with AML, every 6 cycles thereafter unless there is a suspicion of relapse/progression
- For patients with MDS, to be performed as clinically indicated
- When progressive disease is suspected
- The same assessment frequency should carry on post-HSCT
- For Phase 2 Cohort 2 only: bone marrow assessment should be done at C2D1, C4D1, C6D1, and only if relapse is suspected thereafter

Response criteria are derived from the International Working Group (IWG) response criteria for AML (2003) and MDS (2006) where applicable; refer also to Stein et al. 2017.

In general, HSCT is not considered an event in time to event analyses. Patients who stop treatment with FT-2102 to have HSCT will continue to be monitored for duration of response. HSCT is not considered an anti-leukemia therapy for purposes of analyses described herein.

 Table 3
 Response Assessment Criteria

Per Protocol Response Criterion ^{a,b}	Corresponding IWG Response/ Modified Response Criteria		
-	AML (2003)	MDS (2006)	
Morphologic Complete Remission	CR°	CR	
CR with partial hematologic recovery	CRh	Not applicable	
CR with incomplete blood count recovery	CRi	Marrow CR	
Morphologic leukemia-free state	MLFS	Not applicable	
Partial Response	PR	PR	
Stable Disease ^d	Stable Disease ^d	Stable Disease	
Treatment Failure	Progressive disease (PD) e /Relapse	Relapse /PD	

AML = acute myelogenous leukemia; CR = complete remission; CRh = complete response with partial hematologic recovery; CRi = complete remission with incomplete blood count recovery; MLFS = morphologic leukemia-free state; PD = progressive disease; PR = partial response.

Source: Cheson et al. 2003; Cheson et al. 2006; Stein et al. 2017

- Additional response criteria per IWG (e.g., cytogenetic or molecular complete remission) may be collected when available or provided. However, investigators will be asked to provide response assessment corresponding to the per protocol response criteria outlined.

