 - o Not applicable for patients enrolled after Protocol Version 7/ Amendment 6
- Urinalysis (if medically indicated)
- AE monitoring
- Blood sample collection for PK analysis (see Section 6.4 for PK sampling times)
 - o Not applicable for patients enrolled after Protocol Version 7/ Amendment 6
- Blood sample collection for PD analysis (see Section 6.5 for PD sampling times)
 - o Not applicable for patients enrolled after Protocol Version 7/ Amendment 6
- EQ-5D-5L QOL (Phase 2 only)
 - o Not applicable for patients enrolled after Protocol Version 7/ Amendment 6

Cycle 3, Day 1 testing, with the exception of PK/PD, may be done within 72 hours prior to the Day 1 visit.

6.1.20 Cycle 3, Day 15 (Not Applicable for Patients Enrolled after Protocol Version 7/ Amendment 6)

The following procedures should be performed (local laboratory testing allowed):

- Clinical serum chemistries
- CBC with differential and platelet count

6.1.21 Cycle 4, Day 1 (Not Applicable for Patients Enrolled after Protocol Version 7/ Amendment 6)

All procedures to be performed predose:

- Concomitant medication assessment
- Weight
- Vital signs (temperature, blood pressure, pulse rate, and respiratory rate)
- ECOG performance status
- Symptom-directed physical examination
- Serum or urine pregnancy test for female patients of childbearing potential
- 12-lead ECG in triplicate should be conducted within a 10-minute period
- Clinical serum chemistries
- CBC with differential and platelet count

- Bone marrow aspirate or biopsy for disease assessment and cancer-associated mutation analysis:
 - Day 1 on any cycle where response assessment is indicated per Response assessment guidelines (see Section 4.3)
- Urinalysis (if medically indicated)
- AE monitoring
- Blood sample collection for PK analysis Day 1 of every cycle (see Section 6.4 for PK sampling times)
- Blood sample collection for PD analysis Day 1 of every cycle (see Section 6.5 for PD sampling times)
- EQ-5D-5L QOL (Phase 2 only)

Cycle 4: Day 1 testing, with the exception of PK/PD, may be done within 72 hours prior to the Day 1 visit.

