6.1.22 Cycle 5 and Beyond, Day 1 (Every Other Cycle)

Beginning with Cycle 5, patients will return to the clinic every other cycle.

All procedures to be performed predose:

- Concomitant medication assessment
- Weight
- Vital signs (temperature, blood pressure, pulse rate, and respiratory rate)
- 12-lead ECG as clinically indicated
- ECOG performance status
- Symptom-directed physical examination
- Serum or urine pregnancy test for female patients of childbearing potential
- Clinical serum chemistries
- CBC with differential and platelet count
- Bone marrow aspirate or biopsy for response assessment
 - o For patients with AML: Every 6 cycles unless there is an indication of relapse/progression
 - o For patients with MDS: As clinically indicated
 - o For patients enrolled in Phase 2 Cohort 2: Only if there is a suspicion of relapse
- AE monitoring

Cycle 5 and beyond (every other cycle): Day 1 testing may be done within 72 hours prior to the Day 1 visit.

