9.2.4.3 Antileukemic and Antimyelodysplastic Activity

All analysis in the section will be based on patients in the EE Set as the primary analysis, with additional analyses on the FAS, and in some cases the PP Set as supportive.

Primary Efficacy Endpoints and Hypotheses

CR/ CRh Rate

The primary efficacy endpoint for all Phase 2 cohorts, with the exception of Cohort 2, is the CR/CRh rate (defined as bone marrow blasts < 5% with complete (CR) or partial (CRh) hematologic recovery; see Appendix 7 and Appendix 8 for complete definition). The CR/CRh rate will be calculated and presented together with the Clopper-Pearson 95% confidence interval for each cohort.

For Phase 2, Cohort 1, to test the hypothesis that the complete response rate is greater than 15%, a 1-sided exact test for a binomial proportion will be performed. If the exact 1-sided p-value is less than 0.023, the alternative hypothesis will be accepted. This is equivalent to at least 36 CR/CRh responses of 173 EE patients.

For Phase 2, Cohorts 3, 4, and 5 test the hypothesis that the 85% confidence interval for the complete response rate does not include 10%. If there are 5 or more complete responses of the 20 patients in these cohorts, the 85% confidence interval will be greater than 10%, and the alternative hypothesis that the response rate is greater than 10% will be accepted.

Phase 2 Cohorts 6, 7, and 8 are Simon 2-Stage designs and the primary efficacy endpoint will be evaluated via the number of CR/CRh responses stipulated in the design criteria described in Section 9.2.2.

4-Month RFS

The primary endpoint for Phase 2 Cohort 2 is the 4-Month RFS. This will be evaluated by a Simon 2-Stage design described in Section 9.2.2, testing the null hypothesis that the 4-month RFS is < 80%. It is defined as the proportion of patients who have not relapsed or died on or before their 4-month response evaluation. If a patient does not receive a disease response assessment at their 4-month visit but has a subsequent disease response assessment on or after study day 120 that shows non-progression/ non-relapse, they will be evaluated as having achieved 4-month RFS.

Secondary Efficacy Endpoints

CRi, MLFS, Marrow CR, and PR definitions will be derived from the IWG response criteria (see Section 4.3, Appendix 7 and Appendix 8) for AML (2003) and MDS (2006) based on investigator's assessment.

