Admin = administration; AE = adverse event; ALT = alanine aminotransferase; ALP = alkaline phosphatase; AST = aspartate aminotransferase; BUN = blood urea nitrogen; C1D1 = Cycle 1 Day 1; C2D1 = Cycle 2 Day 1; Ca = calcium; CBC = complete blood count; Cl = chloride; ECG = electrocardiogram; ECOG PS = Eastern Cooperative Oncology Group performance status; FSH = follicle-stimulating hormone; K = potassium; LDAC = low dose cytarabine; LDH = lactate dehydrogenase; LH = luteinizing hormone; MDS = myelodysplastic syndrome; Mg = magnesium; Na = sodium; PD = pharmacodynamic; PK = pharmacokinetic; PT = prothrombin time; PTT = partial thromboplastin time; Tx = treatment.

NOTE: All assessments will be conducted predose unless specified otherwise.

- ^a Beginning with Cycle 5, scheduled assessments will be performed every 2 cycles.
- End of Treatment visit to be conducted within 7 days of the decision to discontinue treatment. End of Treatment assessments need not be repeated if they were completed within the previous 2 weeks (4 weeks for bone marrow assessments).
- ^c 28-day Follow-up visit to be conducted within 28 days (+ 7 days) of last dose for adverse event follow-up and to capture initiation of new therapies (con-medications).
- Informed consent must be completed prior to the initiation of any study-specific procedures or assessments. The informed consent process may be completed prior to the Screening Period (i.e., before Day -14) (see Section 6.1.2).
- Includes complete surgical and cardiac history and complete leukemia or MDS medical history. Complete leukemia or MDS medical history will include applicable treatment history as well as cytogenetic risk categorization at diagnosis by NCCN or ELN guidelines.
- Only required in patients enrolled in Phase 1 and patients in Phase 2 participating in Holter monitoring.
- g Height at Screening only.
- Includes temperature, blood pressure, pulse rate, and respiratory rate. Prior to dosing on Days 1, 8, 15, and 22 (Cycle 1); Cycle 2 predose on Days 1 and 15 and Cycle 3 and beyond predose on Day 1.
- Symptom-directed physical examination due to specific findings or abnormalities.

Forma Therapeutics, Inc.

CONFIDENTIAL
August 20, 2020

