- To be performed on all female patients of childbearing potential and within 72 hr of dosing (Day 1 only of every cycle). At Screening, women aged 55 and under, are not surgically sterile, and who are amenorrheic must have LH, FSH, and estradiol measurements within the postmenopausal range for the institution, to be considered of nonchildbearing potential. A serum pregnancy test is required at Screening; serum or urine pregnancy tests are allowed for post-Screening visits.
- Phase 1: Electrocardiograms will be performed in triplicate (within a 10-minute period) predose and at 2 (± 15 minutes), 4 (± 15 minutes), and 8 hr postdose (± 30 minutes) on Cycle 1 Day 1 and Cycle 2 Day 1, and predose at all study visits where indicated. Phase 2: Electrocardiograms will be performed in triplicate (within a 10-minute period) predose on Cycle 1 Day 1 and Cycle 2 Day 1, and at all study visits where indicated. All electrocardiograms will be performed in a supine position.

 Electrocardiograms performed as clinically indicated for Cycle 5 and beyond.
- ^m 24-hour 12-lead continuous Holters will be collected on C1D1 and C2D1 for patients at all centers in the US and select centers ex-US. The Holters should run from approximately 1 hour before dosing until 24 hours (the next day). Patients should remain supine for 10-15 minutes before and 5 minutes after ECG collection. See manual for further guidance on Holter monitoring.
- ⁿ Clinical serum chemistries to include Na, K, Cl, bicarbonate, Mg, Ca, BUN, creatinine, AST, ALT, ALP, albumin, total bilirubin, direct bilirubin (collected only if total bilirubin is abnormal), LDH, glucose, amylase, lipase, uric acid, and thyroid function test (TFT) panel, which includes thyroid-stimulating hormone, free T3, and T4. In addition to the other chemistry panels, TFT panel is to be completed at Screening, C1D1, C2D1, and C3D1, then as clinically indicated.
- ^o May be performed from 48 hr (Cycle 2) or 72 hr (Cycle 3 and 4) prior to Day 1 of a cycle (see Section 6.1).
- P Clinical serum chemistries and CBC with differential and platelet count only at these study visits. May be performed through local laboratory testing.
- ^q Includes hemoglobin, hematocrit, platelets, and white blood cell count with differential.
- ^r Includes PT and PTT.
- Bone marrow aspirate for response assessment as described in Section 4.3. Refer to the laboratory manual for details of sample collection timing.

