Response assessments will be performed through evaluation of clinical findings and bone marrow/peripheral blood cell counts and morphology. Response criteria are derived from the International Working Group (IWG) response criteria for AML (Cheson et al. 2003) and MDS (Cheson et al. 2006) where applicable, and Stein et al. 2017, as outlined in the protocol section 4.3, Appendix 6 and Appendix 7.

Bone marrow for response assessment is required:

- at C2D1 if no peripheral blasts; otherwise, at C3D1, regardless of peripheral blast count;
- at least every 2 cycles (4 to 8 weeks) until morphologic complete remission (CR) is achieved, then up to every 3 cycles (for duration of response assessment) for 12 months after CR achievement, then up to every 6 cycles thereafter;
- when progressive disease is suspected;
- for Phase 2 Cohort 2 only: at C2D1, C4D1, C6D1 and every 6 cycles thereafter.

Response assessment requirements and frequency are the same for all subjects, including those that discontinue treatment due to hematopoietic stem cell transplant (HSCT).

In general, HSCT is not considered an event in time to event analyses. Patients who stop treatment with FT-2102 to have HSCT will continue to be monitored for duration of

response. HSCT is not considered an anti-leukemia therapy for purposes of analyses described herein.

In general, for the purposes of statistical analyses, relapse, progressive disease (PD), or disease progression will be treated interchangeably as being indicative of disease worsening.

AML Response: Following responses for AML will be evaluated by investigator based on the modified Cheson criteria (Cheson et al. 2003). Best overall response for each patient is selected based on the highest category achieved on study from the ordered list in the table below:

		Complete	Overall
Investigator Assessment of AML Response	CR/CRh	Response	Response
Molecular CR (CRm)		$\overline{\mathbf{v}}$	$\overline{\mathbf{v}}$
Cytogenetic CR (CRc)			
Complete Remission (CR)			
CR with Partial Hematologic Recovery (CRh)			
CR with incomplete recovery (CRi)			
Morphologic leukemia-free state (MLFS)			
Partial Remission (PR)			
Clinical Benefit			
Stable Disease			
Resistant Disease			
Relapse			
Progressive Disease (PD)			
Not Evaluable			
Not Done			

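### Cohort 2's 4-month primary endpoint is tied to no scheduled visit, Protocol 6.1.22 drops the C6D1 marrow that 4.3 plans for it, and the synopsis times the stage-1 look differently from 9.2.2.2

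*Protocol*

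**What the plan says.** **Endpoint.** Protocol 9.2.4.3 says of the Cohort 2 primary endpoint: "It is defined as the proportion of patients who have not relapsed or died on or before their 4-month response evaluation". SAP XI.A defines it in the same way. In both, a patient who misses the 4-month visit is credited if a later assessment, on or after study day 120, shows no relapse or progression. No upper limit is set.

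**Marrow schedule.** Protocol 4.3 states for Cohort 2 that "bone marrow assessment should be done at C2D1, C4D1, C6D1, and only if relapse is suspected thereafter". SAP XI.A also includes C6D1: "for Phase 2 Cohort 2 only: at C2D1, C4D1, C6D1 and every 6 cycles thereafter". SAP Appendix 1 (footnote q) lists C6D1 as well and adds C12D1.

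**Visits from Cycle 5.** Protocol 6.1.22 says "Beginning with Cycle 5, patients will return to the clinic every other cycle". Its marrow rule reads "For patients enrolled in Phase 2 Cohort 2: Only if there is a suspicion of relapse". Protocol Appendix 1, footnote a, repeats the visit frequency: "Beginning with Cycle 5, scheduled assessments will be performed every 2 cycles". Its marrow footnote points the other way: "Bone marrow aspirate for response assessment as described in Section 4.3". The marrow footnote of Appendix 2, for patients enrolled after Amendment 6, gives screening and then every 6 cycles, with no Cohort 2 exception.

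**Stage-1 look.** The synopsis times the Cohort 2 futility interim at 11 evaluable patients who have completed their first response assessment. Protocol 9.2.2.2 and SAP IV.C stop the cohort if 9 or fewer of the first 11 are relapse-free at 4 months. SAP VI.G says only that the 11 are evaluable for response, and makes futility stopping binding.

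**The concern.** A binary endpoint at a landmark needs a visit. Here the definition refers to a visit that no schedule contains, and the sections that set the schedule disagree on whether the nearest planned marrow is taken.

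If a site follows 6.1.22, a Cohort 2 patient without suspected relapse has no marrow after C4D1. Relapse in Protocol Appendix 7 can rest on marrow blasts of 5% or more with no blasts in the blood. Such a relapse could be missed, or the patient could reach the endpoint without a marrow-based assessment. Sites following different sections would then be measuring different things.

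The rejection rule leaves little slack: 48 of 53 must be relapse-free, so at most 5 may fail. The choice of visit also matters, because 80% and 94% are stated as 4-month rates and no planned marrow falls at 4 months.

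The synopsis adds a second ambiguity about when the binding stage-1 decision is made.

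**Working it through.** **1. The plan's own figures.** Inputs from Protocol 9.2.2.2: stop if 9 or fewer of 11; otherwise go to 53 and reject if 48 or more; null 0.80, alternative 0.94.

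P(reject) = Σ over x = 10, 11 of Bin(x; 11, p) × P(Bin(42, p) ≥ 48 − x)

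- p = 0.80: 0.2362 × 0.0580 + 0.0859 × 0.1287 = 0.0248. Chance of stopping at stage 1: 1 − 0.2362 − 0.0859 = 0.678.
- p = 0.94: 0.3555 × 0.8948 + 0.5063 × 0.9618 = 0.805.

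Both agree with the stated 0.025 and 80%. The design itself is sound.

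**2. Calendar.** Cycles are 28 days, so CkD1 is Day 28(k − 1) + 1. SAP XI.B sets a month at 30.4375 days, so 4 months is 121.75 days.

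| Visit | Day | Cohort 2 marrow in 4.3 | Cohort 2 in 6.1.22 |
|---|---|---|---|
| C2D1 | 29 | yes | not covered |
| C4D1 | 85 | yes | not covered |
| C5D1 | 113 | no | visit; marrow only if relapse suspected |
| C6D1 | 141 | yes | no visit |
| C7D1 | 169 | no | visit; marrow only if relapse suspected |

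C6D1 is the only marrow planned in 4.3 on or after Day 120. C5D1 is closer to 4 months but falls before Day 120. Under 6.1.22 the first visit after Day 120 is C7D1, with no routine marrow.

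**3. What the choice of visit does.** Assume that 80% and 94% are rates at 121.75 days and that the hazard is constant (the documents give no hazard shape). The rate at Day d is p^(d/121.75). Apply the same 9/11 and 48/53 rule to status at each visit:

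| Visit | Day | Null rate | Alternative rate | Alpha | Power |
|---|---|---|---|---|---|
| C5D1 | 113 | 0.813 | 0.944 | 0.040 | 0.83 |
| 4 months exactly | 121.75 | 0.800 | 0.940 | 0.0248 | 0.805 |
| C6D1 | 141 | 0.772 | 0.931 | 0.008 | 0.735 |
| C7D1 | 169 | 0.734 | 0.918 | 0.001 | 0.62 |

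For C6D1: 0.80^(141/121.75) = 0.772 and 0.94^(141/121.75) = 0.931. Reading at C6D1 is conservative on alpha and costs about 7 points of power (0.805 − 0.735 = 0.070), unless 80% and 94% are justified as rates at that visit.

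**4. Stage-1 timing.** For Cohort 2 the first response assessment in 4.3 is C2D1, Day 29. The rule in 9.2.2.2 and SAP IV.C needs status at 4 months. The two differ by about 93 days (121.75 − 29), or 112 days (16 weeks) if C6D1 is the evaluation.

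**The case against.** **C6D1 is not the only possible evidence.** Assessments also use clinical findings and blood counts (Protocol 4.3), and relapse can show as peripheral blasts or extramedullary disease. The Day-120 fallback is open-ended, and the SAP plans later marrows. This stands in part: a patient can be assessed without the C6D1 marrow. But blood cannot show the marrow-blast criterion, and the C12D1 marrow in the SAP comes at about Day 309.

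**Cross-references favour 4.3.** The Appendix 1 marrow footnote defers to 4.3, and so does 6.1.21 for Cycle 4: "Day 1 on any cycle where response assessment is indicated per Response assessment guidelines (see Section 4.3". The SAP, written to protocol version 5, shows Day 1 visits from Cycle 3 onward without the every-other-cycle limit. Protocol 6.1 says that Amendment 6 introduced the reduced schedule for ongoing patients. This narrows the reach, since patients past C6D1 before that amendment may be unaffected, but 6.1.22 still contradicts 4.3. Protocol 6.1 gives transfers into Cohorts 3 and 6 as its examples for Appendix 2, so Appendix 2 may matter little to Cohort 2.

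**Type I error inflation from a Day-29 look.** A reader might infer that the plan applies the 9/11 cut at Day 29. Under constant hazard that would give alpha of about 0.032. No section states such a rule: 9.2.2.2 and SAP IV.C both use 4-month status, the interim-analysis sections refer back to them, and the synopsis uses the same phrase for Cohort 6. The 0.032 is not a property of this plan.

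**Type I error inflation from unseen relapses.** A reader might also infer that skipping the marrow pushes alpha above 0.025. The documents give no fraction of relapses visible only in marrow. With 80% at 121.75 days and constant hazard, an assumed 10% or 25% of null events between C4D1 and C6D1 going unseen gives alpha 0.011 or 0.019 at Day 141, both below 0.025. A large enough assumed fraction would cross it, but nothing in the documents supports one.

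**Missing assessments and new therapy.** These look undefined but are largely settled. SAP XI.B places the endpoint in the full analysis set, SAP VI.K makes the analysis set the denominator, and SAP XI.B excludes response assessments made after alternate anti-cancer therapy starts. A clarifying sentence would help; there is no real gap.

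**Conclusion.** The point holds as a should-fix matter of consistency and definition. Three things are established from the text alone: no scheduled visit is identified as the 4-month evaluation; 6.1.22 conflicts with 4.3 on the one Cohort 2 marrow planned on or after Day 120; and the synopsis conflicts with 9.2.2.2 and SAP IV.C on the stage-1 look.

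The size depends on which visit is used. The stated design has alpha 0.0248 and power 0.805 for status at the time to which 80% and 94% apply. If status is read at C6D1 and those rates stay at 121.75 days, alpha is about 0.008 and power about 0.74. That rests on the constant-hazard assumption, which is not in the documents. It would be wrong to say that naming C6D1 leaves the operating characteristics unchanged; that is so only if the sponsor justifies 80% and 94% as rates at that evaluation. The documents do not show that the trial's type I error is inflated.

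**What to change.** 1. Reconcile Protocol 6.1.22, Appendix 1 and Appendix 2 with 4.3 so that the C6D1 marrow already planned for Cohort 2 is kept.
2. In Protocol 9.2.4.3 and SAP XI.A, identify which scheduled visit is the 4-month evaluation, and state the time point to which 80% and 94% apply. If C6D1 is chosen and the rates stay at 121.75 days, restate the operating characteristics (about 0.008 and 0.74 under constant hazard). If 0.0248 and 0.805 are to be kept, justify 80% and 94% as rates at that visit.
3. Correct the synopsis so that the stage-1 look uses the first 11 patients' 4-month status, as in 9.2.2.2 and SAP IV.C.
4. As a clarification, say in the endpoint definition that patients in the full analysis set without a qualifying assessment, or who start new anti-cancer therapy beforehand, stay in the denominator and are not counted as relapse-free.

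The cost is wording and schedule-table edits, with no marrow beyond those in 4.3. The real cost lies in item 2: either some power is given up or the benchmarks need a justification that the documents do not now contain. Item 3 adds no delay beyond what 9.2.2.2 already requires.

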5.4 Concomitant Medications

5.4.1 Allowed Medications

Concomitant medications can be administered at the Investigator's discretion according to standard practice during the treatment period. Necessary supportive measures for optimal medical care will be given throughout the study.

Patients who enroll in the study with leukocytosis at baseline or develop leukocytosis after initiation of therapy may receive hydroxyurea. Suggested guidelines for administering hydroxyurea are as follows:

- For a WBC $10 50 \times 10^9$ /L consider administering hydroxyurea 500 mg four times a day
- For a WBC $> 50 \times 10^9$ /L consider administering hydroxyurea 1000 mg four times a day
- Hydroxyurea should be tapered/discontinued when WBC count is $< 10 \times 10^9 / L$

Patients who enroll in the study requiring CNS prophylaxis due to prior CNS involvement and remain asymptomatic may receive intrathecal chemotherapy at the discretion of the investigator. Patients may receive premedication for nausea and/or vomiting at the discretion of the investigator.

Patients may receive antimicrobial treatment or prophylaxis at the discretion of the investigator.

All concomitant medications and supportive therapy administered, starting the first day prior to the first dose and until 28 days after the last dose of FT-2102, must be recorded on the appropriate eCRF page.

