Transfusion independence, defined as the proportion of patients who have received a packed red blood cell or platelet transfusion in the eight weeks prior to first dose of FT-2102 who have a 28-day period during any point on study with no transfusion required. Additionally, the number of patients who are transfusion independent for at least 56 consecutive days will also be summarized. Percent of transfusion independence will be calculated based on the number of patients who were transfusion dependent prior to first dose of FT-2102.

For each cohort, the number and percentage of the best overall response will be presented by response category and by treatment group. Other binomial endpoints including overall response rate (CR + CRh + CRi + MLFS + PR) and rate of responses in the individual response category, will also be analyzed. Number and percentage of patients within each response category will be presented by dose/dosing schedule and visit. Clopper-Pearson 95% confidence intervals will be provided along with the responses.

Overall survival for all cohorts at landmark timepoints will be analyzed.

Time to event data will be analyzed using Kaplan-Meier (KM) methods for each cohort. The median time will be tabulated along with the 95% Brookmeyer Crowley confidence intervals. The estimated probability of survival over time will be plotted as KM curves for each cohort (or by disease type and by treatment).

Detailed considerations for all time to event variables are provided in the SAP.

Additional efficacy analyses will be specified in the SAP.

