For a patient with none of these events before the end of study follow-up, EFS will be censored as per Table 1. For patients lost to follow-up prior to any evidence of event, the EFS data will be censored at their last completed assessment date that is SD or better prior to the initiation of anti-cancer therapy.

Overall survival (OS): OS is defined as the time in months from the first dose of study drug until death from any cause. For patients who are not known to have died by the end of study follow-up, OS will be censored on the date the patient was last known to be alive.

Transfusion independence (TI): Patients will be classified as "dependent" or "independent" at baseline within each category of platelets, pRBC, any (i.e., receiving either platelets or pRBC or both) and both (i.e., receiving both platelets and pRBC) if they received a transfusion within 8 weeks prior to the first dose of FT-2102. TI will be defined as patients who experience at least a 28-day or 56-day period during any point on treatment with no transfusion of that type required. For the "both" category, patients who are classified as dependent must have received both a platelet and pRBC transfusion within the 8 weeks prior to baseline, and to be classified post baseline as independent, they must experience a 28 or 56 day minimum duration on study where they did not require a transfusion of either platelets or pRBC.

B. Efficacy Analysis

Any response assessment occurring after the start of alternate anti-cancer therapy will not be included in the analyses using response assessments.

Note that some patients who were assigned to single agent therapy in Phase 1 requested to start combination therapy with azacitidine when a response was not observed on single agent treatment. In such cases, upon beginning dosing with azacitidine (if the patient was assigned to single agent therapy), then response assessments occurring after the first dose of azacitidine will not be included in efficacy analyses. Time to event analyses for such instances will be treated as if the patient has experienced disease progression when azacitidine is initiated.

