- 4. Patients with subsequent anti-cancer therapies prior to an event date will be considered as having an event as the start of the anti-cancer therapy.
- 5. Patients who didn't have an event and are still on treatment will be censored at the last treatment date, otherwise will be censored at the last response assessment.

For DOR and DCR HSCT sensitivity analysis will be performed, where patients who undergo HSCT will be censored at the last adequate assessment prior to HSCT. The following subgroup analyses will be performed:

• CR/CRh rate, ORR, DCR/CRh – For AML patients in the EE analysis set: AML type (primary or secondary), disease state (relapsed/refractory or treatment naive), AML cytogenetic risk classification, IDH1 mutation type, IDH1 mutation confirmed by

central lab, age group, sex, region, race, baseline ECOG PS, prior HSCT for AML, prior HMA, prior IDH1 therapy, and prior FT-2102 therapy.

• OS, EFS – For AML patients in the FAS analysis set: AML type (primary or secondary), disease state (relapsed/refractory or treatment naive), AML cytogenetic risk classification, IDH1 mutation type, IDH1 mutation confirmed by central lab, age group, sex, region, race, baseline ECOG PS, prior HSCT for AML, prior HMA, prior IDH1 therapy, and prior FT-2102 therapy.

Kaplan Meier plots will not be produced for subgroup analyses.

Transfusion Independence

Transfusion independence will be analyzed as part of the clinical benefit expected from FT-2102. The percentage of patients who are transfusion dependent at baseline will be summarized (overall and by type of blood product of RBC and/or platelets). The proportion of patients who became transfusion independent during any 28-day and 56-day period during treatment will be summarized by best overall response on study. Percentages will be based on the number of patients within the best overall response category.

Swim Lane Plot of Time on Treatment and Duration of Response

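### Transfusion independence is judged over time on study in the protocol and in one SAP category, but over time on treatment in the rest of the SAP

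*Protocol*

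**What the plan says.** Protocol section 3 lists TI among the Phase 2 secondary measures of clinical benefit. Protocol 9.2.4.3 takes patients transfused with red cells or platelets in the eight weeks before first dose and counts those "who have a 28-day period during any point on study with no transfusion required". It adds a 56-day version.

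SAP XI.A sets up four categories: platelets, pRBC, *any* (either product or both) and *both* (both products). Its general rule is "at least a 28-day or 56-day period during any point on treatment with no transfusion of that type required". The next sentence, on *both*, says of independence after baseline that "they must experience a 28 or 56 day minimum duration on study where they did not require a transfusion of either platelets or pRBC". SAP XI.B, under Transfusion Independence, summarises patients who became "transfusion independent during any 28-day and 56-day period during treatment". The second swim lane plot in XI.B changes the bar colour when 28-day TI is reached, on a bar whose length is time on treatment.

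On data collection, protocol 5.4.1 covers "All concomitant medications and supportive therapy administered", from the day before first dose "until 28 days after the last dose of FT-2102, must be recorded". Transfusions are not named. Survival follow-up (protocol 6.1.26) collects survival status and other antineoplastic therapy.

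**The concern.** One endpoint has two observation windows, and they are not close to each other. Protocol 8.2.1 says that stopping treatment need not mean leaving the study. A patient can therefore be on study long after the last dose, having had a transplant or another regimen, or being contacted only about every three months for survival.

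Two things are at stake. The rows of one SAP table would be built on different windows, so *both* could not be compared with platelets, pRBC or *any*. And where the on-study wording is followed, TI can credit FT-2102 with transfusion-free time that came after the drug was stopped, although SAP XI.B presents TI as clinical benefit expected from FT-2102.

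**Working it through.** The documents state no TI rate, power or sample size, so there is no figure to reproduce. The check sets the texts side by side and then counts days.

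**1. The windows**

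| Place | Applies to | Window |
|---|---|---|
| Protocol 9.2.4.3 | red cells or platelets | on study |
| SAP XI.A, general definition | all categories | on treatment |
| SAP XI.A, *both* sentence | *both* | on study |
| SAP XI.B, Transfusion Independence | all, no exception given | during treatment |
| SAP XI.B, second swim lane plot | 28-day TI | bar is time on treatment |

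**2. What this does inside the SAP table**

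- Baseline: *both* requires both products, and *any* requires at least one. Every patient in *both* is therefore in *any*.
- After baseline: for *any*, no transfusion of that type means neither product. For *both*, neither product is stated outright. The test is the same.
- With one window, a patient independent in *both* must be independent in *any*.
- With two windows, that fails. Take a patient dependent on both products who is transfused with each at intervals shorter than 28 days throughout treatment, stops for HSCT, and later goes 28 days without a transfusion while still on study. This patient is not independent for platelets, pRBC or *any*, but is independent for *both*.

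This step needs no assumption about how transfusions are recorded.

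**3. How much time on study lies after treatment**

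Inputs: expected treatment of about 26 weeks, or 182 days (protocol synopsis, Duration); 28 days of further recording (5.4.1); survival follow-up of up to 36 months from C1D1 in Phase 2 and 12 months in Phase 1 (6.1.26); 30.4375 days per month (SAP XI.B).

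- Phase 2: 36 × 30.4375 − 182 − 28 = 885.8 days, room for 31 consecutive 28-day periods or 15 consecutive 56-day periods.
- Phase 1: 12 × 30.4375 − 182 − 28 = 155.2 days, room for 5 or 2.

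**4. The conditional risk from unrecorded time**

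Suppose that transfusion recording ends with the 5.4.1 period, and that no record is read as no transfusion. A wholly unrecorded qualifying period is then complete at day 28 + 28 = 56 after last dose for 28-day TI, and at day 28 + 56 = 84 for 56-day TI.

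Let t be the true on-treatment TI rate and s the share of the remaining patients who are alive and on study at that day. The apparent rate is t + (1 − t) × s, so the excess is (1 − t) × s. The documents give neither t nor s. As a pure assumption, take exponential survival from last dose with a median of m months and every survivor staying on study. Then s = exp(−ln 2 × d / (m × 30.4375)):

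| m (assumed) | d = 56 | d = 84 |
|---|---|---|
| 1 month | 28% | 15% |
| 3 months | 65% | 53% |
| 6 months | 81% | 73% |

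These are survival probabilities. For each assumed median they are a ceiling on the excess from wholly unrecorded periods. They do not estimate bias in this trial. With the window limited to treatment and to recorded time, the excess is 0.

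**The case against.** The strongest reply is that the SAP already settles the window. Its introduction says that it governs the analysis. The general definition comes first and uses treatment time, XI.B repeats this without an exception, and the swim lane plot agrees. On that view the *both* sentence only adds that both products are involved, and *on study* is loose wording. This largely stands: under the SAP the exposure is one row. It does not remove the point, because the *both* sentence is the only specific post-baseline rule for that category, and a programmer may fairly follow the specific rule over the general one.

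A reader might infer that transfusions are recorded only until 28 days after last dose. The documents do not establish that. Protocol 5.4.1 speaks of supportive therapy, and its period starts one day before first dose, so it cannot supply the eight-week look-back that TI needs. Some other transfusion record may exist. AML complete remission also requires transfusion independence (Appendix 7), so some status may be known at response assessments after treatment (6.1.25).

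A reader might also infer that patients alive off treatment become independent by default. No passage says that an absent record means no transfusion, and SAP VI.C says that missing data are not imputed unless stated. It is equally true that no passage limits TI to periods with transfusion records.

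Full records would not cure the problem. SAP XI.B drops response assessments after alternate anticancer therapy, but that rule is written for response assessments, and HSCT is not treated as anti-leukemia therapy (XI.A). On-study time would still include periods after transplant and after later regimens.

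**Conclusion.** The conflict is explicit and should be corrected. It lies between protocol 9.2.4.3 and the SAP, and inside SAP XI.A. With the SAP governing, its direct effect is that the *both* row can count patients as independent who are not independent in *any*. The effect would be general only if the protocol wording were followed.

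The size of any inflation cannot be derived from the documents. It requires the on-study window to be used, qualifying periods to fall after treatment and, for the unrecorded-time mechanism, absent records to be read as no transfusion. The survival percentages above hold only under those conditions and an assumed median.

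TI is secondary and descriptive, with no multiplicity control (SAP VI.H). No primary test, sample size or stopping rule depends on it.

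**What to change.** In the SAP XI.A sentence on *both*, and in protocol 9.2.4.3, replace *on study* with *on treatment*, so that all four categories share one window. Add one derivation rule to SAP XI.A: a 28- or 56-day period counts only if it lies wholly within the time for which transfusions were recorded for that patient.

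The cost is two wording changes and one programming rule, with no new data. The reported TI rate may be slightly lower.
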